The **Randomization Phase** will consist of a Treatment Period and a Follow-up Period. It will begin at the time of randomization of the first subject and will consist of 28-day blinded study treatment cycles. The data cutoff for the primary analysis will occur at the end of the Randomization Phase, which is defined as when the last subject enrolled completes the Week 24 tumor assessments or discontinues study treatment if before Week 24.

Subjects on treatment at the time of data cutoff for the primary analysis will remain on blinded investigational product until the primary analysis has been completed and will continue to receive investigational product until they complete the Off-treatment visit prior to their transition to commercial lenvatinib (if commercially available for that individual subject) or through an access program administered by the sponsor. While receiving investigational product, subjects should continue with the same assessments as noted in the Schedule of Assessments/Procedures. The last subject's last assessment (Off-treatment visit) will be the **End of Study**.

Subjects will be randomly assigned to treatment with 1 of 2 blinded dosages of lenvatinib in a 1:1 ratio.

- The Treatment Period for an individual subject will begin at the time of randomization and will end upon completion of the Off-treatment Visit, which will occur within 30 days after the final administration of study drug. Serious adverse events (SAEs) must be captured for 28 days after the last dose of study drug. Subjects will undergo safety and efficacy assessments as defined in the Schedule of Procedures/Assessments and will continue to receive study treatment until disease progression.
- The Follow-up Period will begin immediately after the Off-treatment Visit and will continue as long as the subject is alive, unless the subject withdraws consent, or until the data cutoff for primary analysis. Subjects who discontinue study drug treatment prior to disease progression will

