The data cutoff for the primary analysis will occur at the end of the Randomization Phase, which is defined as the time the last subject enrolled completes the Week 24 tumor assessments or discontinues study treatment before Week 24. Subjects will remain on blinded investigational product until the primary analysis has been completed and, after study unblinding. Subjects will continue to receive investigational product until they complete the Off-treatment visit prior to their transition to commercial lenvatinib or an access program. The last subject last visit for the **End of Study** will be the date of the Off-treatment visit for the last subject. At the End of Study, the Sponsor (or investigator where required) will ensure that all relevant IRBs/IECs and Competent Authorities are notified about the study completion per regulatory requirements in each country or region.

In the case of early termination/temporary halt of the study, the investigator should notify the IRB/IEC and Competent Authority within 15 calendar days, and a detailed written explanation of the reasons for the termination/halt should be given.

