This study consists of 2 phases, the Prerandomization Phase and the Randomization Phase. An overview of the study design is presented in [Figure 1](#). The average estimated duration of each subject's participation is 18 months. The data cutoff for the primary analysis will occur when the last subject enrolled completes the Week 24 tumor assessments or discontinues study drug before Week 24. Therefore, the last subject enrolled will be on study for 24 weeks. Subjects on treatment at this time will remain on blinded investigational product until the primary analysis has been completed. After the primary analysis is completed, subjects still receiving treatment will be able to continue taking lenvatinib through their pharmacy (if commercially available for that individual subject) or through an access program administered by the sponsor. Following study unblinding, subjects will continue to receive investigational product until they complete the Off-treatment visit prior to their transition to commercial lenvatinib or an access program. The last subject last visit for the **End of Study** will be the date of the Off-treatment visit for the last subject.

The treatment assignments of all subjects randomized and treated in Study 211 prior to Amendment 03 were unblinded as of 26 Aug 2016. Following unblinding, these subjects were treated with open-label lenvatinib study drug at the dose determined at the discretion of the investigator until they were transitioned to commercial lenvatinib drug product or an access program in their country. Adverse event data were collected for each of these subjects until they transitioned to lenvatinib treatment outside the study.

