### 9.1.2 Randomization Phase

The **Randomization Phase** will consist of a Treatment Period and a Follow-up Period. It will begin at the time of randomization of the first subject and will consist of 28-day blinded study treatment cycles. The data cutoff for the primary analysis will occur at the end of the Randomization Phase, which is defined as when the last subject enrolled completes the Week 24 tumor assessments or discontinues study treatment before Week 24. Subjects on treatment at this time will remain on blinded investigational product until the primary analysis has been completed. After study unblinding, subjects will continue to receive investigational product until they complete the Off-treatment visit prior to their transition to commercial lenvatinib or an access program. The last subject last visit for the **End of Study** will be the date of the Off-treatment visit for the last subject.

Subjects will be randomly assigned to treatment with 1 of 2 blinded dosages of lenvatinib in a 1:1 ratio.

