### 9.3.3 Removal of Subjects From Therapy or Assessment

The investigator may discontinue study treatment or withdraw the subject from the study at any time for safety or administrative reasons. The subject may decide to discontinue study treatment or withdraw from the study at any time for any reason. The reason for discontinuation will be documented. If a subject discontinues study treatment, the subject will enter the Follow-up Period and complete protocol-specified off-treatment visits, procedures, PFS2 and survival follow-up unless the subject withdraws consent. The investigator should confirm whether a subject will withdraw from study treatment but agree to continue protocol-specified, off-treatment study visits, procedures, and PFS2 and survival follow-up, or whether the subject will withdraw consent. If a subject withdraws consent, the date will be documented in the source documents. The Discontinuation From Treatment CRF page will be completed indicating the primary reason for discontinuation and all other reason(s) contributing to the subject's discontinuation from treatment. In addition, the date of last dose of study drug will be recorded on the Study Drug Dosing CRF page.

During the Follow-up Period, subjects who have discontinued study treatment without disease progression should continue to have tumor assessments performed every 8 weeks until disease progression is documented, another anticancer therapy is initiated, or the data cutoff for primary analysis.

All subjects will be followed for survival until death, except where a subject withdraws consent or until the data cutoff for the primary analysis.

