## 9.7 Statistical Methods

All statistical analyses will be performed by the sponsor or designee after the study is completed (based on the data cutoff for the primary analysis) and the database is locked and released for unblinding. Statistical analyses will be performed using SAS software or other

validated statistical software as required. Details of the statistical analyses will be included in a separate SAP.

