3.2 Overall Study Design and Plan

This was a multicenter, randomized, double-blind study being conducted as a postmarketing commitment to the US Food and Drug Administration (FDA) and the European Medicines Agency (EMA) to evaluate whether there was a lower starting dosage of lenvatinib other than 24 mg QD that could provide comparable efficacy but have a better safety profile in subjects with RR-DTC with radiographic evidence of disease progression (PD) within the prior 12 months.

Eligible subjects should have measurable disease according to Response Evaluation Criteria in Solid Tumors Version 1.1 (RECIST 1.1) and evidence of PD within 13 months before signing informed consent (both assessed by independent radiologic review) and were randomly assigned to treatment in a 1:1 ratio to receive lenvatinib 24 mg or 18 mg orally QD. The total sample size is 152 subjects (76 subjects per arm). Randomization was stratified by age (≤ 65 years or >65 years) and Eastern Cooperative Oncology Group (ECOG) performance status (PS) of 0 vs 1 or 2. Study ended when the last subject enrolled completed the Week 24 tumor assessments or discontinued study drug before Week 24. Subjects received study treatment until disease progression, development of unacceptable toxicity, subject requested to discontinue, withdrew consent or was lost to follow-up, end of the study, or until study termination by the sponsor. After PD was observed, subjects were followed for PFS2 and survival.

This study consisted of 2 phases: the Prerandomization/Pretreatment Phase and the Randomization/Treatment Phase (see Figure 1). The Schedules of Procedures and Assessments for both study phases are explained in Table 7 of Protocol Amendment 05. Per protocol, tumor assessments were performed during the Prerandomization Phase and then every 8 weeks (within the 8th week) from the date of randomization during treatment cycles in the Randomization Phase. Subjects who discontinued treatment without PD in the Randomization Phase continued to undergo tumor assessments every 8 weeks until PD was documented or another anticancer therapy was initiated. Subjects were then followed every 12 weeks (± 1 week) for survival, PFS2 and all subsequent anticancer treatments received (unless this information was not allowed to be provided due to confidentiality) had been recorded until the End of Study.

[figure not shown]

Figure 1. Study Design for Study E7080-G000-211 (as of Protocol Amendment 05)

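### The primary-analysis cutoff can be triggered when the last-enrolled subject stops study drug early, leaving recent enrollees with less than 24 weeks for both 24-week primary endpoints (conditional; small expected effect)

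*Protocol*

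**What the plan says.** The Protocol Synopsis (Study Design) ends the Randomization Phase, and with it the data for the primary analysis, at a point "which is defined as when the last subject enrolled completes the Week 24 tumor assessments or discontinues study treatment if before Week 24". Protocol 5.1, 9.1 and 9.1.2 repeat this either/or rule. SAP 3.2 has it as well: "Study ended when the last subject enrolled completed the Week 24 tumor assessments or discontinued study drug before Week 24". Protocol 9.1 then concludes: "Therefore, the last subject enrolled will be on study for 24 weeks".

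Both primary endpoints use a fixed window of 24 weeks from randomisation (Protocol 9.7.1.1.1, SAP 5.1.1). Protocol 9.7 places the statistical analyses "after the study is completed (based on the data cutoff for the primary analysis".

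Subjects still on drug at the cutoff "will remain on blinded investigational product until the primary analysis has been completed", with their scheduled assessments continuing. For subjects off drug without progression, Protocol 9.3.3 continues scans "until disease progression is documented, another anticancer therapy is initiated, or the data cutoff for primary analysis", and 9.5.1.2.4 agrees. Table 7 footnote r and Protocol 9.5.4 describe the same scans without naming the cutoff.

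No section makes the cutoff wait for the other subjects to reach Week 24. SAP 5.3.5 refers to SAP 5.4 for missing ORR data, but 5.4 contains no such rule.

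**The concern.** One subject's early stop, for any reason, can fix the calendar date at which the whole trial is read. Subjects randomised shortly before that one may then have had one or two of the three scheduled scans (Weeks 8, 16 and 24), or none, and only part of the 24-week adverse-event window. Those without a response or a Grade 3+ event by then are not true Week 24 non-responders or non-events. Their window is simply unfinished, and the SAP does not say how to classify them.

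The conclusion in Protocol 9.1 that the last subject has 24 weeks on study shows what was intended, but it does not follow from the discontinuation branch in the sentence before it. At stake are the accuracy of both primary endpoint rates and, possibly, the behaviour of the noninferiority test at its margin.

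**Working it through.** **The plan's own figures (Protocol 9.7.2).**
- Margin: 21.4^(-0.30) = 0.399, stated as 0.40.
- Sample size per arm: (1.960+0.842)² × 2/(0.544×0.456) / (ln 0.4)² = 75.4, so 76.
- Power at 76 per arm: 80.3%.
- Safety half-width: 1.96 × √(2×0.705×0.295/76) = 14.5%, stated as about 15%.

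All reproduce, so the sample-size arithmetic is not in question.

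**Accrual (assumption).** The documents give no accrual period. The Synopsis range of 6 to 42 months on treatment implies about 36 months. Rate = 152/(36×30.4375/7) = 0.971 per week (1.165 at 30 months, 0.832 at 42).

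**Subjects short of 24 weeks** = (24-t) × rate.
- Week 8 stop: 16 × 0.971 = 15.5 (13.3-18.6 for 42-30 months).
- Week 16 stop: 8 × 0.971 = 7.8 (6.7-9.3).

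**Missed responders.** Let w8 be the share of Week 24 responders already seen at Week 8, assumed 56-70%. The lower value is 50%/89%, from the 2-month median time to response and the 89% of eventual responders seen by 6 months (Protocol 7.1). That median stands in a sentence on dose-reduced subjects, so 56% is used only as a floor. Let s24 be the share first seen at Week 24, taken as 25-75% of 1-w8. Unobserved time counts as no response, and all 152 stay in the denominator.
- Week 8 stop: 0.971 × 0.544 × (8(1-w8) + 8·s24). Low: 0.528 × (2.40+0.60) = 1.6. High: 0.528 × (3.52+2.64) = 3.3. Divided by 152: 1.0-2.1 points.
- Week 16 stop: 0.528 × 8·s24 = 0.528 × 0.60 to 0.528 × 2.64 = 0.3-1.4. Divided by 152: 0.2-0.9 points.

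**Missed Grade 3+ events.** The rate is 70.5% by Week 24 (Protocol 9.7.2). Onset is taken as constant hazard, λ = -ln(0.295)/24 = 0.0509 per week, or as uniform.
- Constant hazard: 0.971 × [(e^(-λt) - 0.295)/λ - 0.295(24-t)] = 2.5 (Week 8), 0.5 (Week 16).
- Uniform: 0.971 × 0.705 × (24-t)²/48 = 3.7 (Week 8), 0.9 (Week 16).
- Divided by 152: 1.6-2.4 points and 0.4-0.6 points.

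**Power at a true OR of 1.** With both rates reduced alike: 80.4-80.6%, against 80.3%.

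**Type I error at a true OR of 0.4** (54.4% vs 32.3%; Wald log OR, 76 per arm; 2.50% with no loss). L is the fraction of responders lost.

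| Stop | L, 24 mg | L, 18 mg | Apparent OR | Type I error |
|---|---|---|---|---|
| Week 8, equal loss | 1.9-3.9% | 1.9-3.9% | 0.405-0.411 | 2.7-3.0% |
| Week 8, w8 70% on 24 mg, 56% on 18 mg | 2.3% | 3.4% | 0.400 | 2.50% |
| Week 8, w8 70% on 24 mg, 50% on 18 mg | 2.3% | 3.8% | 0.397 | 2.38% |

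The last two rows split the later responses evenly between Weeks 16 and 24. With the 70%/56% pair, a Week 16 stop also gives 2.50% and a Week 4 stop gives 2.81%. The result therefore depends on the time of the stop as well as on response timing by dose.

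**Chance of the trigger.** Take the 18.3-month median PFS of Study 303 (Protocol 7.1) as exponential. P(progression or death) = 1 - exp(-ln2 × months/18.3): 6.7% by Week 8 and 13.0% by Week 16. Expected missed responders = 0.067 × (1.6 to 3.3) + 0.063 × (0.3 to 1.4) = 0.1-0.3, or 0.1-0.2 points of ORR. Toxicity and withdrawal stops would add to this. The documents give no rate for them.

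**The case against.** The intent is plain: Protocol 9.1 expects 24 weeks for the last subject, and the Synopsis gives 6 months as the shortest time on treatment. A sponsor might simply wait. Moreover, no passage says outright that later data are excluded from ORR at 24 weeks. SAP 8.4 applies the cutoff date explicitly to PFS and OS, and on-drug subjects continue to be assessed. This has some force, since the exclusion is inferred from Protocol 9.7. But it is the ordinary meaning of a data cutoff, no text admits later data, and the stated intent conflicts with the rule as written.

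The effect is also small. That stands. Even under equal loss, the average type I error over progression or death alone is 2.52-2.55%. Exact binomial enumeration with no loss already gives 2.58%, so the shift is smaller than the gap between the two methods.

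A reader might infer two stronger points. The first is that truncation makes noninferiority easier to declare. That needs both arms to lose the same proportion of responders. The documents give no response timing by dose, and later responses on 18 mg can cancel or reverse the shift. The second is that the Grade 3+ difference shrinks in the same proportion as the rates. Under constant hazard with 70.5% against an assumed 60%, a Week 8 stop lowers the rates by 2.3% and 2.6% in relative terms, but their difference by only 0.9%.

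**Conclusion.** The defect is real but conditional. As written, an early stop by one subject can truncate both primary endpoints for roughly 8 to 16 recent enrollees, for stops between Week 16 and Week 8. Both endpoint rates would then be understated by at most about 2.4 points. This rests on about 36 months of uniform accrual, the assumed response and event timing, and counting unobserved time as no response or no event, which the SAP does not specify.

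The documents do not support a claim of lost power, a direction for the type I error, or a proportional shrinking of the safety difference. The expected effect is small. The point is worth raising because the rule contradicts Protocol 9.1's own conclusion and is cheap to correct.

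**What to change.** In the Protocol Synopsis, 5.1, 9.1 and 9.1.2, and in SAP 3.2, define the cutoff as the date when every randomised subject has completed the Week 24 tumor assessment or has had 24 weeks plus a stated scan window since randomisation, whether on or off study drug. Delete the clause triggered by the last subject's discontinuation. The window could be the 1 week per visit already built into the missed-visit rule of SAP Table 4. The sentence in 9.1 about the last subject's 24 weeks should be reworded to match.

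The cost is one sentence in each place, with no extra subjects and no new procedures. If the last subject stops at week t, then the cutoff, unblinding, the existing 12-weekly survival and PFS2 follow-up, and the existing 8-weekly off-drug scans run at most 24-t weeks plus the window longer. That is about one scan window beyond the Week 24 branch the plan already accepts.

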#### **Number of Subjects**

Prior to Amendment 03, approximately 300 subjects were planned to be screened to provide 210 randomized subjects (70 per arm). A total of 56 subjects were screened and 41 of these subjects were randomized and treated until study enrollment was temporarily halted. Efficacy and safety data for these initial 41 randomized subjects until they transitioned to lenvatinib treatment outside the study will be reported separately.

As of Amendment 03.1, an additional 180 subjects will be screened to provide 152 randomized subjects (76 per arm).

#### **Inclusion Criteria**

1. Subjects must have histologically or cytologically confirmed diagnosis of one of the following differentiated thyroid cancer (DTC) subtypes:
  - a. Papillary thyroid cancer (PTC)
    - Follicular variant
    - Variants (including but not limited to tall cell, columnar cell, cribriform-morular, solid, oxyphil, Warthin's-like, trabecular, tumor with nodular fasciitis-like stroma, Hürthle cell variant of papillary carcinoma, poorly differentiated)
  - b. Follicular thyroid cancer (FTC)
    - Hürthle cell
    - Clear cell
    - Insular
2. Measurable disease meeting the following criteria and confirmed by central radiographic review:
  - a. At least 1 lesion of  $\geq 1.0$  cm in the longest diameter for a non-lymph node or  $\geq 1.5$  cm in the short-axis diameter for a lymph node that is serially measurable according to RECIST 1.1 using computed tomography/magnetic resonance imaging (CT/MRI). If there is only 1 target lesion and it is a non-lymph node, it should have a longest diameter of  $\geq 1.5$  cm.
  - b. Lesions that have had external beam radiotherapy or locoregional therapies such as radiofrequency (RF) ablation must show evidence of progressive disease based on RECIST 1.1 to be deemed a target lesion.

3. Subjects must show evidence of disease progression within 12 months (an additional month will be allowed to accommodate actual dates of performance of screening scans, ie, within  $\leq 13$  months) prior to signing informed consent, according to RECIST 1.1 assessed and confirmed by central radiographic review of CT and/or MRI scans.
4. Subjects must be  $^{131}\text{I}$ -refractory/resistant as defined by at least one of the following:
  - a. One or more measurable lesions that do not demonstrate iodine uptake on any radioiodine scan.
  - b. One or more measurable lesions that have progressed according to RECIST 1.1 within 12 months (an additional month will be allowed to accommodate actual dates of performance of screening scans, ie, within  $\leq 13$  months) after  $^{131}\text{I}$  therapy, despite demonstration of radioiodine avidity at the time of that treatment by pre- or posttreatment scanning. These subjects must not be eligible for possible curative surgery.
  - c. Cumulative activity of  $^{131}\text{I}$  of  $>600$  mCi or 22 gigabecquerels (GBq), with the last dose administered at least 6 months prior to study entry.
5. Subjects with known brain metastases who have completed whole brain radiotherapy, stereotactic radiosurgery or complete surgical resection, will be eligible if they have remained clinically stable, asymptomatic, and off steroids for one month.
6. Subjects must be receiving thyroxine suppression therapy and TSH should not be elevated (TSH should be  $\leq 5.50$  mIU/mL). When tolerated by the subject, thyroxine dose should be changed to achieve TSH suppression (TSH  $<0.50$  mIU/mL) and this dose may be changed concurrently upon starting study drug treatment.
7. All chemotherapy- or radiation-related toxicities must have resolved to Grade  $<2$  severity per Common Terminology Criteria for Adverse Events (CTCAE v4.03), except alopecia and infertility.
8. Subjects must have an ECOG performance status of 0, 1 or 2.
9. Adequately controlled blood pressure (BP) with or without antihypertensive medications, defined as BP  $\leq 150/90$  mmHg at Screening and no change in antihypertensive medications within 1 week prior to Cycle 1/Day 1.
10. Adequate renal function defined as calculated creatinine clearance  $\geq 30$  mL/min per the Cockcroft and Gault formula.
11. Adequate bone marrow function:
  - a. Absolute neutrophil count (ANC)  $\geq 1500/\text{mm}^3$  ( $\geq 1.5 \times 10^3/\mu\text{L}$ )
  - b. Platelets  $\geq 100,000/\text{mm}^3$  ( $\geq 100 \times 10^9/\text{L}$ )
  - c. Hemoglobin  $\geq 9.0$  g/dL
12. Adequate blood coagulation function as evidenced by an International Normalized Ratio (INR)  $\leq 1.5$  (except for subjects on warfarin therapy where INR may be  $\geq 2$  and  $<3$ ).
13. Adequate liver function:
  - a. Bilirubin  $\leq 1.5 \times$  upper limit of normal (ULN) except for unconjugated hyperbilirubinemia or Gilbert's syndrome.
  - b. Alkaline phosphatase, alanine aminotransferase (ALT), and aspartate aminotransferase (AST)  $\leq 3 \times$  ULN ( $\leq 5 \times$  ULN if subject has liver metastases). If alkaline phosphatase is  $>3 \times$  ULN (in absence of liver metastases) or  $>5 \times$  ULN (in presence of liver metastases) AND the subject also is known to have bone metastases, the liver-specific alkaline phosphatase must be separated from the total and used to assess the liver function instead of total alkaline phosphatase.
14. Males or females age  $\geq 18$  years at the time of informed consent.

15. Females must not be lactating or pregnant at Screening or Baseline (as documented by a negative beta-human chorionic gonadotropin [ $\beta$ -hCG] test with a minimum sensitivity of 25 IU/L or equivalent units of  $\beta$ -hCG). A separate baseline assessment is required if a negative screening pregnancy test was obtained more than 72 hours before the first dose of study drug.
16. All females will be considered to be of childbearing potential unless they are postmenopausal (amenorrheic for at least 12 consecutive months, in the appropriate age group and without other known or suspected cause) or have been sterilized surgically (ie, bilateral tubal ligation, total hysterectomy or bilateral oophorectomy, all with surgery at least 1 month before dosing).
17. Females of childbearing potential should avoid becoming pregnant and use highly effective contraception while on treatment with lenvatinib and for at least 1 month after finishing treatment. Females of childbearing potential must not have had unprotected sexual intercourse within 30 days before study entry and must agree to use a highly effective method of contraception (eg, total abstinence, an intrauterine device, a contraceptive implant, an oral contraceptive, or have a vasectomized partner with confirmed azoospermia) throughout the entire study period and for 30 days after study drug discontinuation. Females who are using hormonal contraceptives must have been on a stable dose of the same hormonal contraceptive product for at least 4 weeks before dosing and must continue to use the same contraceptive during the study and for 30 days after study drug discontinuation. Women using oral hormonal contraceptives should add a barrier method.
18. Subject must voluntarily agree to provide written informed consent.
19. Subject must be willing and able to comply with all aspects of the protocol.

